8.2. Secondary Efficacy Analysis

The secondary efficacy analyses will be conducted to ensure that the family-wise error rate is controlled using the Holm method for multiplicity adjustment. The following are the relevant secondary analyses of interest:

(Between-Treatment Testing)

1. The change in percent of wound surface area with clean, healthy, viable tissue (%) at the Day 4-6 interim visit relative to baseline between the treatment arms.
2. The change in percent of wound surface area with clean, healthy, viable tissue (%) at the Day 2-3 interim visit relative to baseline between the treatment arms.
3. Percent change in total wound area (%) from baseline to Day 6-9 upon the final dressing removal between the treatment arms
4. Percent change in total wound area (%) from baseline to Day 4-6 between the treatment arms
5. Percent change in total wound area (%) from baseline to Day 2-3 between the treatment arms
6. Percent change in total wound volume (%) from baseline to Day 6-9 upon the final dressing removal between the treatment arms
7. Percent change in total wound volume (%) from baseline to Day 4-6 between the treatment arms
8. Percent change in total wound volume (%) from baseline to Day 2-3 between the treatment arms
9. Physician assessment of the need for surgical debridement upon completion of study treatment up to Day 6-9

(Within-Treatment Testing)

10. Within-treatment-arm changes in percent of wound surface area assessed as clean, healthy, viable tissue (%) at the Day 6-9 visit to baseline for VFCC arm.
11. Within-treatment-arm changes in percent of total wound area (%) at the Day 6-9 visit to baseline for VFCC arm.
12. Within-treatment-arm changes in percent of total wound volume (%) at the Day 6-9 visit to baseline for VFCC arm.

8.2.1. Change in percent of wound surface area with healthy/viable/clean tissue relative to baseline

The analysis conducted as primary analysis will be repeated for Day 4-6 and Day 2-3 results. These analyses will be carried out for the mITT and FAS (with NOCB/LOCF imputation).

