### **8.6. Interim Analysis**

A nonbinding, unblinded interim analysis will be performed when approximately 30 evaluable subjects have had their assessments for the primary endpoint (percent change on wound bed surface area considered to be clean, healthy and viable from baseline to

Day 6-9). The purpose of the interim analysis is to evaluate the need for early stopping due to futility, efficacy, and/or sample size re-calculation.

The primary endpoint will be analyzed as outlined in Section 8.3.4. If the resulting p-value for the primary analysis is less than  $\alpha=0.006$  as determined utilizing the O'Brien-Fleming  $\alpha$ -spending function (O'Brien 1979), the null hypothesis will be rejected, and the study may be stopped for efficacy.

If the null hypothesis could not be rejected, conditional power will be calculated to assess for futility and/or sample size adjustment. If the conditional power is lower than the pre-specified boundary in the interim SAP, the trial may be stopped for futility. If the conditional power is above the futility boundary, the conditional power will be evaluated utilizing methods described in Chen et al (Chen 2004) to determine if a sample size increase is required.

The final analysis will be conducted at  $\alpha=0.048$  to maintain the overall type I error rate at  $\alpha=0.05$  as determined by the O'Brien-Fleming spending function. Details of the interim analysis will be described in the interim SAP before the interim analysis is conducted.

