6.1. Interim Analysis

A non-binding, unblinded interim analysis will be performed when approximately 30 evaluable Subjects have had their assessments for the primary endpoint (percent change on wound bed surface area considered to be clean, healthy, and viable from baseline to Day 6-9). The purpose of the interim analysis is to evaluate the need for early stopping due to futility, efficacy, and/or sample size re-estimation.

Details of the planned analyses to occur at interim are outlined in the interim Statistical Analysis Plan (SAP) document: CLIN-PROT-SAP-05-813629.

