8. EFFICACY ANALYSIS

8.1. Primary Efficacy Analysis

The primary endpoint is the change in the percent of wound bed surface area (cm^2) considered to be clean, healthy, and viable from baseline to Day 6-9 upon the final dressing removal. The percentage of clean, healthy, and viable tissue (pctCHV) is defined as the sum of percentages of viable Bone/Cartilage/Ligament/Tissue (B/C/L/T), viable fat, viable muscle/fascia, and granulation tissue. The change in percent (ΔpctCHV) of clean, healthy, and viable tissue from baseline to Day 6-9 upon the final dressing removal is defined as:

$$\Delta\text{pctCHV} = \text{pctCHV}_4 - \text{pctCHV}_0$$

where,

pctCHV₀ = percent of clean, healthy, and viable tissue at baseline

pctCHV₄ = percent of clean, healthy, and viable tissue at Day 6-9 upon final dressing removal.

The following hypothesis will be tested:

Null: $\Delta\text{pctCHV}_{\text{VFCC}} - \Delta\text{pctCHV}_{\text{Control}} = 0$
 $\neq 0$

Alternative: $\Delta\text{pctCHV}_{\text{VFCC}} - \Delta\text{pctCHV}_{\text{Control}}$

where $\Delta pctCHV_{VFCC} - \Delta pctCHV_{Control}$ is the difference of the change in percent of wound bed surface area (cm^2) considered to be clean, healthy, and viable between the VFCC with NPWTi-d group and the Control group.

Generalized linear modeling will be used to analyze the primary endpoint with the following fixed effects: clinical site; baseline percent of wound bed surface considered clean, healthy and viable [pctCHV0]; body mass index [BMI]; treatment arm and indicator of baseline wound undermining.

If any of the covariates (except treatment arm and site ID) is not statistically significant at the 0.1 level, then the non-significant term(s) will be removed from the model and the updated model will be re-run. The analysis will be conducted at the α -level determined by the O'Brien-Fleming α -spending function² and observed fraction time.

```
proc mixed data=adeff;
  class trtp siteid undermin;
  model chg=bmi base trtp siteid undermin / ddfm=kr cl;
  lsmeans trtp/ diff cl;
run;
```

The analysis will be conducted at a final alpha level as determined by the O'Brien-Fleming α -spending function². The primary analysis will be based on the mITT analysis set, and the test of the difference of the least square means estimates.

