8.2.2. Percent change in total wound area (cm^2) relative to baseline

The percent change in total wound area ($\Delta\text{pctArea}$) from baseline to Day X upon the final dressing removal is defined as the difference in total wound area between the Day X assessment and baseline assessment, divided by the baseline value and multiplied by 100.

$$\Delta pctArea = \left(\frac{AreaX - Area0}{Area0} \right) \times 100$$

where,

Area0 = the total wound area at baseline

AreaX = the total wound area at Day X (e.g. Day 6-9) upon final dressing removal.

The following hypothesis will be tested:

Null: $\Delta pctArea_{VFCC} - \Delta pctArea_{Control} = 0$
 $\neq 0$

Alternative: $\Delta pctArea_{VFCC} - \Delta pctArea_{Control}$

where $\Delta pctArea_{VFCC} - \Delta pctArea_{Control}$ is the difference of percent change in total wound area (cm^2) between the VFCC with NPWTi-d group and Control group.

The appropriate generalized linear modeling will be used to analyze the endpoint with potential fixed effects: clinical site; baseline total wound area; body mass index [BMI]; treatment arm and indicator of baseline wound undermining. These analyses will be carried out for the mITT and FAS (with NOCB/LOCF imputation).

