1	Section 8.1 Primary Efficacy Analysis. Added the option to pursue a proportional odds model if appropriate.	Accounts for the possible situation of severe violation of the normality assumption in the final linear model for the primary analysis.
1	
Section 8.2 Secondary Efficacy Analysis and Section 8.3 Exploratory Analysis.
 
Identified 12 relevant secondary analyses of interest: three (3) within-treatment testing for the VFCC arm only and nine (9) between treatment arm testings. Outlined a Holm method of multiplicity adjustments in these secondary testing.
 
Changed formulas for percent change in area, percent change in volume, percent change in granulation, absolute change in area, absolute change in volume and absolute change in granulation to be consistent with primary endpoint definition such that negative values represent reductions and positive values increases with the passage of time.
 
Added six (6) within-VFCC tests and nine (9) within-Collagenase tests as exploratory analyses.
 
Modified statistical test used for categorical data analysis to Fisher's exact test rather than Chi-square or Fisher's exact test (if the sample size in any subgroup is less than 5).
	To add important clarifying details
1	Section 8.3.6 and 8.3.7. Clarified the percent granulation tissue in formula is based on the percent viable granulation tissue derived from the tissue typing work done by the independent assessor from the wound images.	Clarified input variable in the formulas with percent granulation tissue.
1	Sections 9.2 and 9.3. Added statements in both sections to describe the statistical test (namely, Fisher's Exact test) to be carried out for between-treatment differences in the adverse event and medication summaries.	Specify the appropriate test for differences.

Statistical Analysis Plan

CLIN-PROT-SAP-05-830770

Version: 1

Status: Release

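### SAP 8.2 controls error within its 12 secondary tests by Holm, but leaves open whether that family depends on the primary, at what alpha, and (for 11 tests) on which analysis set

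*SAP*

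**What the plan says.** **Primary.** Protocol 8.6 sets 0.006 at the interim and 0.048 at the final analysis "to maintain the overall type I error rate at" 0.05. SAP 8.1 gives no number: "The analysis will be conducted at a final alpha level as determined by" the O'Brien-Fleming spending function. The hypothesis is two-sided and the analysis set is mITT. SAP 8.1 lists the FAS and Per-Protocol repeats as supportive.

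**Secondaries.** SAP 8.2 says that these analyses are done "to ensure that the family-wise error rate is controlled using the Holm method for multiplicity adjustment". The revision history (SAP 12) counts them: "Identified 12 relevant secondary analyses of interest: three (3) within-treatment testing for the VFCC arm only and nine (9) between treatment arm testings". The primary is not on the list. Items 1 and 2 are the primary measure at Day 4-6 and Day 2-3. Item 10 is the primary measure at Day 6-9, tested within the VFCC arm against its own baseline.

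**Analysis sets.** SAP 8.2.1 to 8.2.4 run the models on two sets. SAP 8.2.2, for example, says: "These analyses will be carried out for the mITT and FAS (with NOCB/LOCF imputation". SAP 8.2.5 bases the debridement test on mITT and treats the other sets as supportive.

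**Not stated in either document.** Whether the Holm family is tested only after the primary is rejected, the alpha for that family, and which of the two sets supplies the Holm p-values for the other 11 tests.

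**The concern.** Holm limits the error inside the list it is given. Here the list leaves out a primary test that already has its own 0.05. With no link between the two, each family can spend up to about 5%, and the efficacy results taken together can carry more than 5% error when nothing differs between the arms.

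The content of the list makes this matter. If the Day 6-9 comparison failed, the plan as written would still allow a multiplicity-adjusted result for the same measure at Day 2-3 or Day 4-6. It would also allow an adjusted within-VFCC result that can reject without any difference between arms. With two sets available for 11 hypotheses and none named for Holm, the choice could be made after both results are known, and Holm does not cover that choice.

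**Working it through.** **1. The plan's own figures.** The documents give no combined error rate to reproduce, so I checked the figures that set the scale.

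- Sample size (Protocol 8.4.1: 20 v 40 points, SD 22, Wilcoxon, about 80% power). Noether's formula is n = (z_α/2 + z_β)² / [6(p − 0.5)²], with p = Φ(20/(22√2)) = 0.740. At two-sided 0.05, n = (1.960 + 0.842)² / [6(0.740 − 0.5)²] = 22.74, rounded up to 23. Power at 23 per group is 80.4%. The stated 23 is reproduced.
- Primary alpha. The interim "will be performed when approximately 30 evaluable Subjects have had their assessments for the primary endpoint", so the information fraction is 30/60 = 0.50 or 30/46 = 0.65. The pair 0.006/0.048 gives an overall 0.0504 at 0.50 and 0.0493 at 0.65. The primary therefore uses essentially the whole 0.05.

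**2. Count of tests with an unnamed Holm set.** SAP 8.2.1 has 2 tests, 8.2.2 has 3, 8.2.3 has 3 and 8.2.4 has 3, which makes 11. Debridement is the twelfth.

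**3. Joint error by formula.** Assume Holm at 0.05, the primary at an overall 0.05, and all nulls true.

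- Upper bound: 0.05 + 0.05 = 10.0%.
- Independent tests: Holm rejects something when the smallest p-value is below 0.05/12, so its error is 1 − (1 − 0.05/12)¹² = 4.89%. The joint error is 1 − 0.95 × (1 − 0.0489) = 9.6%.

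**4. Joint error by simulation.** The primary and the 12 tests were drawn as multivariate normal, 400,000 runs per setting, with the within-arm tests sharing the VFCC estimate. The documents give no correlations, so the values are assumed. The primary is treated as one test at 0.05, without modelling the interim look.

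| Correlation between endpoints | Between adjacent visits | Holm family alone | Primary or any secondary | In favour of VFCC only | Secondary rejected, primary not | With a gate on the primary |
|---|---|---|---|---|---|---|
| 0 | 0.5 | 4.5% | 8.8% | 4.6% | 3.9% | 4.9% |
| 0.3 | 0.5 | 4.5% | 8.7% | 4.5% | 3.7% | 5.0% |
| 0.3 | 0.8 | 4.0% | 7.9% | 4.2% | 3.0% | 5.0% |
| 0.6 | 0.8 | 3.6% | 7.4% | 4.1% | 2.4% | 5.0% |
| 0.6 | 0.9 | 3.3% | 7.0% | 3.9% | 2.0% | 5.0% |

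With both correlations at zero and only the shared VFCC estimate linking tests, the joint figure is 9.2%. Putting both families at 0.048 gives 6.7% to 9.3% (the upper figure for independent tests). The nominal rate in one direction is 0.05/2 = 2.5%.

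**5. The within-VFCC test.** Suppose VFCC gains only the 20 points that the protocol assumes for collagenase. With SD 22 and n = 23, z = 20/(22/√23) = 4.36. Holm's first step, 0.05/12 = 0.0042 two-sided, needs z of about 2.87. Item 10 is then likely to reject with no difference between arms. That would be a true finding about change from baseline, but it says nothing about the comparison with collagenase. Rejecting all three within-arm tests would also ease the first threshold for the nine between-arm tests from 0.05/12 to 0.05/9 = 0.0056. With real within-VFCC changes, the joint false-rejection rate is 7.2 to 9.1%.

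**The case against.** The case for leaving the text alone has real force.

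- The sentence in SAP 8.2 is about the secondary analyses, and Holm delivers what it says for them. The 0.05 in Protocol 8.6 concerns the primary across its two looks. A reader might infer that the SAP promises 5% over primary and secondaries and then breaks the promise. The documents contain no such promise. This stands in full.
- The SAP does not state that the secondaries are tested whatever the primary shows. It is silent, so the right word is unspecified. This stands, but silence still leaves the analyst free to proceed that way.
- A reader might infer that every secondary hypothesis lacks a designated set. That is wrong for debridement (SAP 8.2.5, and Protocol 8.3.5.3 agrees). For wound area and volume, Protocol 8.3.5.1 and 8.3.5.2 follow the primary's approach, which is mITT. SAP 8.2.1 repeats the primary analysis, also mITT. So mITT is the natural reading, but SAP 8.2.1 to 8.2.4 name both sets without ranking them.
- A reader might infer that an early-visit result may replace a failed primary. Nothing says so: SAP 4.1.1 fixes one primary at Day 6-9, and the early visits are labelled secondary. The risk is one of presentation.
- Controlling the primary and secondary families separately is a recognised choice, and this is a post-market study of devices used within their cleared labelling. That is fair, but a plan that makes that choice should state it.

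**Conclusion.** The point holds as a gap in specification. SAP 8.2 controls error within its 12 tests. It does not tie them to the primary, state their alpha, or name the Holm set for 11 of them.

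With Holm at an assumed 0.05 and the primary at an overall 0.05, the two-sided chance of at least one false rejection with all nulls true is about 7 to 9.6%. False findings in favour of VFCC account for about 4 to 5%, against 2.5% nominal. These figures rest on an alpha and correlations that the documents do not give, and they do not include the extra choice between mITT and FAS. The excess arises only if the primary null is true. If the primary effect is real, false secondary claims are bounded by Holm's own level. The range should not be read as contradicting a number in the plan. Label: cheap improvement.

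**What to change.** Add to SAP 8.2:

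> The Holm procedure is applied at two-sided 0.05 to the mITT results, and only if the primary null hypothesis is rejected; otherwise secondary p-values are descriptive. FAS results are supportive.

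In the simulation this brings the joint error back to about 5% (4.9 to 5.1%). Because that check does not model the interim look, the authors should also confirm that the level stated for the secondaries suits a stop for efficacy at the interim.

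The cost is a few sentences and no new data. The real downside is that no secondary result can be claimed as confirmatory when the primary fails. The change has to precede final database lock, because SAP 1 rules out amendment after that point. A later correction could only be reported as a deviation in the study report.

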8.2.2. Percent change in total wound area (cm^2) relative to baseline

The percent change in total wound area ($\Delta\text{pctArea}$) from baseline to Day X upon the final dressing removal is defined as the difference in total wound area between the Day X assessment and baseline assessment, divided by the baseline value and multiplied by 100.

$$\Delta pctArea = \left(\frac{AreaX - Area0}{Area0} \right) \times 100$$

where,

Area0 = the total wound area at baseline

AreaX = the total wound area at Day X (e.g. Day 6-9) upon final dressing removal.

The following hypothesis will be tested:

Null: $\Delta pctArea_{VFCC} - \Delta pctArea_{Control} = 0$
 $\neq 0$

Alternative: $\Delta pctArea_{VFCC} - \Delta pctArea_{Control}$

where $\Delta pctArea_{VFCC} - \Delta pctArea_{Control}$ is the difference of percent change in total wound area (cm^2) between the VFCC with NPWTi-d group and Control group.

The appropriate generalized linear modeling will be used to analyze the endpoint with potential fixed effects: clinical site; baseline total wound area; body mass index [BMI]; treatment arm and indicator of baseline wound undermining. These analyses will be carried out for the mITT and FAS (with NOCB/LOCF imputation).

8.2.3. Percent change in total wound volume (cm^3) relative to baseline

The percent change in total wound volume ($\Delta pctVol$) from baseline to Day X upon the final dressing removal is defined as the difference in total wound area between the Day X assessment and baseline assessment, divided by the baseline value and multiplied by 100.

$$\Delta pctVol = \left(\frac{VolX - Vol0}{Vol0} \right) \times 100$$

where,

Vol0 = the total wound volume at baseline

VolX = the total wound volume at Day X (e.g. Day 6-9) upon final dressing removal.

The following hypothesis will be tested:

Null: $\Delta pctVol_{VFCC} - \Delta pctVol_{Control} = 0$
 $\neq 0$

Alternative: $\Delta pctVol_{VFCC} - \Delta pctVol_{Control}$

where $\Delta pctVol_{VFCC} - \Delta pctVol_{Control}$ is the difference of percent change in total wound volume (cm^3) between the VFCC with NPWTi-d group and Control group.

The appropriate generalized linear modeling will be used to analyze the endpoint with potential fixed effects: clinical site; baseline total wound area; body mass index [BMI]; treatment arm and indicator of baseline wound undermining. These analyses will be carried out for the mITT and FAS (with NOCB/LOCF imputation).

8.2.4. Within-VFCC-Treatment Arm Testing

The appropriate generalized linear modeling will be used to analyze the primary or secondary endpoint (percent change in wound area considered clean/viable/healthy, total wound area, and wound volume) with the following potential fixed effects: clinical site; baseline total wound area; body mass index; treatment arm; and indicator of baseline wound undermining.

The within-arm testing will be based on the least square means estimate for the VFCC treatment arm derived from the final model used for the between-treatment testing in the primary or secondary analyses. These analyses will be carried out for the mITT and FAS (with NOCB/LOCF imputation).

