4.1.3. Exploratory Endpoint(s)

The exploratory endpoints for this study include:

- Repeated measures of the change in percent of clean, healthy, viable tissue (%) over time, analyzing the rate of change and differences at study visits.
- Repeated measures of the percent change in total wound volume (%) over time, analyzing the rate of change and differences at study visits.
- Repeated measures of the percent change in total wound area (%) over time, analyzing the rate of change and differences at study visits.
- The absolute change from baseline to Day 6-9 upon the final dressing removal in the wound bed surface area (cm^2) considered to be clean, healthy, and viable.
- The absolute change from baseline to Day 6-9 in the total wound area (cm^2).
- The absolute change from baseline to Day 6-9 in the total wound volume (cm^3).
- Repeated measures of the absolute change in total wound volume, total wound area and viable wound area over time, analyzing the rate of change and differences at study visits.
- The percent change and absolute change of granulation tissue from baseline to Day 6-9 upon the final dressing removal
- Number of treatment applications and/or dressing changes per Subject (i.e., collagenase ointment applications versus VFCC applications); analyzed by treatment duration, wound size, and/or wound type, as appropriate.
- Total time to perform treatment applications and/or dressing changes per Subject; analyzed by wound size and/or wound type, as appropriate.
- Within-VFCC-treatment changes in the percent of wound bed surface area considered clean, healthy, viable tissue (%) at Day 2-3 and Day 4-6 study visits relative to baseline.
- Within-VFCC-treatment changes in the percent of total wound area (%) at Day 2-3 and Day 4-6 study visits relative to baseline.
- Within-VFCC-treatment changes in the percent of wound volume (%) at Day 2-3 and Day 4-6 study visits relative to baseline.

- Within-Collagenase-control-treatment changes in the percent wound surface area considered clean, healthy and viable; changes in percent wound area; and changes in percent wound volume at all study visits relative to baseline.

In addition to these exploratory endpoints, the following data will be collected from Subjects in one of the groups:

- Total number of collagenase ointment tubes used per Subject; analyzed by treatment duration, wound size, and/or wound type, as appropriate.

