6.2. Determination of Sample Size

The study will randomize approximately 60 Subjects from approximately 15 sites in a 1:1 ratio to either the V.A.C. VERAFL0 CLEANSE CHOICE™ (i.e., Treatment) arm or the collagenase ointment (i.e., Control) arm. Sample size determination is based on the primary endpoint. It was estimated that slough reduced by almost 20% in the Tender Wet 24 group and 10% in the Iruxol N group in M. Konig et al.¹ Assuming a 20% increase in clean, healthy, viable wound bed surface area in the collagenase ointment group and a 40% increase in clean, healthy, viable wound bed surface area in the VFCC and NPWTi-d group, and a typical standard deviation of 22%, 23

evaluable Subjects per group would provide approximately 80% power to detect a statistically significant difference using the Wilcoxon Rank-Sum test (nQuery Advisor® 7.0).

In some circumstances, even though the investigator assessed the wound to have $\leq 2/3$ area of clean, healthy, and viable wound bed, it may not meet the requirement when assessed by the independent assessor if measured by a 3D camera. Such Subjects will be excluded from the mITT for the analysis of the primary endpoint. To allow for this possibility, plus the possibility that some Subjects may be lost to follow-up prior to their post-baseline assessment at the Day 6-9 visit, the sample size is increased to a total of 60 randomized Subjects (i.e., 30 Subjects per arm). This accounts for an approximately 23% drop out rate.

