8.3.3. Additional Within-VFCC-Arm-Testing and Within-Collagenase-Control-Arm-Testing

The appropriate generalized linear modeling will be used to analyze the primary or secondary endpoint (percent change in wound area considered clean/viable/healthy, total wound area, and wound volume) with the following potential fixed effects: clinical site; baseline total wound area; body mass index; treatment arm; and indicator of baseline wound undermining.

The within-arm testing will be based on the least square means estimate for the VFCC or Collagenase treatment arm derived from the final model used for the between-treatment testing in the primary or secondary analyses. This exploratory testing will occur in conjunction with the within-VFCC-treatment arm testing described previously in section 8.2.4. This testing plan will examine within-VFCC and within-collagenase changes in percent wound surface area assessed as clean, healthy and viable; percent total wound area, and percent wound volume at all study visits relative to baseline. These analyses will be carried out for the mITT and FAS (with NOCB/LOCF imputation).

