12. REVISION HISTORY

The purpose of this appendix is to describe modifications made to this document. The final SAP V1.0 was written using a legacy KCI template and approved via DocuSign on 03August 2020. The changes described below cover the conversion to the current 3M SAP template and other changes to the content of the original document.

Revision History Table		
Ver- sion #	Description of change including section number impacted	Reason for change
1	Release	Initial Version
1	Deleted appendix that detailed the planned Tables, Listings and Figures (TLFs) for the final study report.	Copied planned TLFs into a separate word document. This is a communication tool for the biostatistician, statistical programmer, and other stakeholders that is not needed in ENOVIA.
1	Section 3.4 Blinding covers the blinding of independent assessor in assessing wound images and blinding of the biostatisticians and programmer prior to interim analysis.	Document all blinding occurring in this study.
1	Section 4.1.1 Modified the primary endpoint statement from: “percent change in the wound bed surface area (cm ²) considered to be clean, healthy, and viable from baseline to Day 6-9 upon the final dressing removal” to the following: “change in the percent of wound bed surface area (cm ²) considered to be clean, healthy, and viable from baseline to Day 6-9 upon the final dressing removal”.	We not computing a percent change but computing a difference or change in the derived percent of wound surface area considered clean, healthy, and viable.
1	Section 4.1.2 Added the following endpoints: change in percent of clean, healthy viable tissues, and percent change in total wound area and wound volume at interim visits relative to baseline, and not just at end of study (Day 6-9) relative to baseline. Added within-VFCC-treatment arm testing at 6-9 day visit relative to baseline for the same endpoints we are testing for between-treatment-arm differences.	To evaluate potential differences detected at interim visits (Day 2-3 and Day 4-6); and to evaluate potential differences of within-VFCC-arm testing.
1	Section 4.1.3 Added exploratory analysis on using repeated measures analyses of the primary and secondary endpoints;	To add important detail to account for

Revision History Table

Ver-sion #	Description of change including section number impacted	Reason for change

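### Three VFCC-only change-from-baseline tests sit in the Holm family while the matching collagenase tests are exploratory; separately, the volume and granulation models adjust for baseline area instead of the outcome's own baseline

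*SAP*

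**What the plan says.** **Within-arm tests.** SAP 8.2 states that the "family-wise error rate is controlled using the Holm method for multiplicity adjustment" and then lists twelve tests. Tests 1-9 compare the arms. Tests 10-12 concern the VFCC arm alone at Day 6-9: viable tissue (test 10, "Within-treatment-arm changes in percent of wound surface area assessed as clean, healthy, viable tissue"), wound area (test 11) and wound volume (test 12). SAP 8.2.4 gives the method: "The within-arm testing will be based on the least square means estimate for the VFCC treatment arm derived from the final model".

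The collagenase counterparts are exploratory. SAP 4.1.3 lists "Within-Collagenase-control-treatment changes in the percent wound surface area considered clean, healthy and viable", with area and volume, at all visits. SAP 8.3.3 adds: "This exploratory testing will occur in conjunction with the within-VFCC-treatment arm testing described previously in section 8.2.4". None of the three secondary endpoints in Protocol 3.3 is a within-arm test. The SAP logs the addition openly in its Revision History: "Added within-VFCC-treatment arm testing at 6-9 day visit relative to baseline". SAP 8.2 states neither a family alpha nor a condition on the primary test.

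**Volume and covariates.** SAP 8.2.3 describes percent change in volume in words as a difference in wound area, although its formula uses VolX and Vol0. Its listed baseline covariate is total wound area. The same covariate is listed for absolute volume change (8.3.6) and change in percent granulation (8.3.7). The primary model (8.1) and the area model (8.2.2) use the baseline of their own outcome.

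**The concern.** The stated objective (SAP 2) is a comparison of two treatments. A test of one arm against zero cannot address it, because wounds in either arm may improve. The plan itself expects the control arm to improve: "Assuming a 20% increase in clean, healthy, viable wound bed surface area in the collagenase ointment group". In addition, the mITT set keeps only wounds whose measured baseline is at most two-thirds viable (SAP 5.4). Selection on a measured baseline can push later values upward in both arms. A between-arm contrast removes that shift; a one-arm test does not.

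The stake is in reporting. If the treatments work equally well, the trial could still present a multiplicity-controlled significant VFCC result beside a non-significant primary, with the equivalent collagenase result labelled only exploratory.

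The volume point is smaller. The prose contradicts the formula, and the models leave out the baseline value that would normally be adjusted for.

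**Working it through.** **Inputs.** From SAP 6.2: gains of 20% (collagenase) and 40% (VFCC), SD 22%, 23 evaluable per group, and "The study will randomize approximately 60 Subjects from approximately 15 sites in a 1:1 ratio". From Protocol 8.6: final primary alpha 0.048. From SAP 8.1: site and arm always stay in the model; other covariates are dropped if not significant at 0.1. Assumed: family alpha 0.05; 20% read as 20 points, in line with the difference definition in SAP 8.1.

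**The plan's own figure.** Noether's formula for the rank-sum test, two-sided 0.05:
- p = Φ(20/(22√2)) = 0.740
- N = (1.960 + 0.842)² / (3 × (0.740 − 0.5)²) = 45.5, so 23 per group, with power 0.804
- 46/(1 − 0.23) = 59.7, so 60 randomised

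The sample size reproduces.

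**Holm's first step.** 0.05/12 = 0.00417 with twelve tests; 0.05/9 = 0.00556 with nine. The first is the strictest threshold test 10 can face, so with family alpha 0.05 the rejection rates below are floors.

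**Simple check without sites, equal gain in both arms.** Noncentrality = gain/(22/√23).

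| Common gain | Noncentrality | P(test 10 significant), df 22 | df 44 |
|---|---|---|---|
| 20 | 4.36 | 0.860 | 0.901 |
| 15 | 3.27 | 0.540 | 0.600 |
| 10 | 2.18 | 0.188 | 0.216 |

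**Planned model, simulated (8,000 trials per cell).** Sixty subjects were randomised in permuted blocks of 4 within 15 sites (block size assumed), and 46 were kept at random. Both arms had the same mean and SD 22, with no true site differences. The model had fixed effects for site, arm, BMI, baseline and undermining, with the last three dropped if p ≥ 0.1. The VFCC least-squares mean was tested at 0.05/12 and the primary at 0.048.

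| Result | Common gain | Even sites | Moderately uneven | Very uneven |
|---|---|---|---|---|
| Test 10 significant | 20 | 0.839 | 0.737 | 0.696 |
| | 15 | 0.529 | 0.415 | 0.388 |
| | 10 | 0.193 | 0.142 | 0.132 |
| Test 10 significant, primary not | 20 | 0.803 | 0.701 | 0.665 |
| | 15 | 0.497 | 0.387 | 0.364 |
| | 10 | 0.170 | 0.121 | 0.113 |
| Both significant | 20 | 0.036 | 0.036 | 0.031 |

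The last row is what a gate on the primary would let through. If baseline explained 20% of the variance (assumed), the first row would be 0.902, 0.818 and 0.791.

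Tests 11 and 12 cannot be sized, because the documents give no planning values for area or volume.

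**Covariates side by side.**

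| SAP section | Outcome | Baseline covariate listed |
|---|---|---|
| 8.1 | Change in percent viable | Percent viable |
| 8.2.2 | Percent change in area | Area |
| 8.2.3 | Percent change in volume | Area |
| 8.3.6 | Absolute change in volume | Area |
| 8.3.7 | Change in percent granulation | Area |
| 8.2.4, 8.3.3 | Viable tissue, area, volume, within arm | Area for all three |

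The last row conflicts with its own section for viable tissue: the estimate is said to come from the final between-arm model, which in 8.1 uses baseline percent viable. The precision to be gained from baseline volume cannot be computed from the documents.

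**The case against.** The strongest reply is that nothing here is a statistical error. Holm controls the error rate for all twelve nulls. In the scenarios above the VFCC arm truly improves, so each rejection of test 10 is correct; with no true change it would reject in about 0.4% of trials (0.05/12). A gate lowers the rate almost by construction, since with equal arms few trials have a significant primary. All of that stands: the percentages measure how often a non-comparative result would be available to report, not a false-positive rate.

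The SAP also limits misreading. It prints tests 10-12 under their own within-treatment label, logs the addition, pre-specifies the collagenase analyses with the same models and analysis sets, and makes VFCC's own earlier-visit within-arm tests exploratory too. The objective cited is the primary one, which a secondary endpoint need not answer. This narrows the asymmetry to three Day 6-9 tests but does not remove it.

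The cost to the between-arm tests is small: if tests 10-12 reject first, the other nine start at alpha/9 either way.

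On volume, the heading, formula and hypotheses all say volume, so the sentence is a slip. The covariate lists in these secondary and exploratory sections are called potential effects, and adjusting for area does not bias a randomised comparison. These points also stand. Even so, baseline volume and baseline percent granulation are already measured and are not among the listed options.

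**Conclusion.** The concern holds and is minor. Three single-arm tests have multiplicity-controlled secondary status for one arm only, and rejecting them cannot support a claim of VFCC over collagenase. With equal true gains of 20 points, test 10 would be significant in 70-84% of trials under the planned model; this falls to 39-53% at 15 points and 13-19% at 10. These figures rest on SD 22, 46 evaluable subjects, a family alpha of 0.05, reading the planning percentages as points, and the assumed block size, site sizes and absence of site differences.

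The primary conclusion and the validity of Holm are not affected. The covariate choice in 8.2.3, 8.3.6 and 8.3.7 is an avoidable inconsistency, not a source of bias. The wording in 8.2.3 and the lists in 8.2.4 and 8.3.3 are editorial corrections.

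**What to change.** 1. Move tests 10-12 from SAP 4.1.2 and 8.2 to 4.1.3 and 8.3.3, beside the collagenase analyses. Report the mean change with a confidence interval for both arms, labelled descriptive. Apply Holm to tests 1-9.
2. Optionally, test 1-9 only if the primary is significant. If the sponsor keeps tests 10-12 in 8.2, a condition that the primary be significant is the minimum safeguard for them.
3. Use baseline total wound volume in 8.2.3 and 8.3.6, and baseline percent granulation in 8.3.7.
4. Correct the definition in 8.2.3 so that it refers to volume.
5. In 8.2.4 and 8.3.3, make the covariate list match the between-arm model being reused, with baseline percent viable for viable tissue.

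No change is proposed for 8.3.4 or 8.3.8, where baseline area is a component of the outcome.

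The cost is SAP wording. The sponsor gives up three secondary labels; no analysis or data are lost.
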